7 TREATMENT OF SUBJECTS

Shield TX (UK) Limited will provide ferric maltol and matching placebo to all study sites. Sites must arrange storage of Investigational Medicinal Product (IMP) in a temperature monitored, secure location which is accessible to authorized individuals only.

7.1 INVESTIGATIONAL MEDICINAL PRODUCT (IMP) PRESENTATION

Ferric maltol is presented as a hard, gelatin, red capsule, 19 mm long x 7 mm diameter (size 1). Each capsule contains 30 mg iron and the following excipient(s) with known effect: 91.5 mg of lactose, 0.5 mg of Allura Red AC (E129) and 0.3 mg Sunset Yellow FCF (E110). A full list of excipients can be found in the Investigator's Brochure.

Placebo will be provided identical in appearance to ferric maltol hard, gelatin, red capsules and the same excipients with the active substance replaced with the primary excipient lactose.

7.2 PACKAGING

The product will be supplied in a white polypropylene securitainer with a tamper evident standard securitainer cap of white medium density polyethylene. An appropriate number of bottles containing 56 capsules will be provided to cover intervals between study visits.

7.3 STORAGE

IMP must be stored below 25 °C (77 °F) and must not be refrigerated or frozen. In the event that the drug is exposed to temperatures greater than or equal to 25°C, the Sponsor should be contacted for review and further instruction.

7.4 LABELLING

All kits and bottles will be identified by a unique kit number for the double-blind treatment period. Kits and bottles for the open-label treatment period will be clearly labelled as ferric maltol.

Labels of the IMP will contain information according to 21CFR Section 312.6.

7.5 DISPENSATION

Specific containers will be allocated to specific subjects via the central IXRS/randomization system for dispensation according to the treatment randomly allocated during the 16 week double-blind treatment period.

7.6 ADMINISTRATION

Eligible subjects will be randomized to receive one of the following treatments for the first 16 weeks of the study:

- Oral ferric maltol, 30 mg capsule bid.
- Oral matching placebo capsule bid.

Following 16 weeks of randomized treatment, all subjects will receive open-label treatment with ferric maltol for up to an additional 36 weeks.

Subjects should be instructed to take one capsule of ferric maltol (or placebo) twice daily, morning and evening, on an empty stomach (with half a glass of water), as the absorption of iron is reduced when taken with food.

If a subject forgets to take a dose he/she should take the next dose as normal. Do not take a double dose to make up for a forgotten capsule.

7.7 TREATMENT COMPLIANCE

Subjects will be instructed to take the study drug as described in detail on the drug labels and by the study site. Subjects will be instructed to return all unused supplies and all clinical study medication packaging at each visit. The delivery of medication to the site, its use and return, as well as subject-specific compliance, will be reconciled and documented using a Drug Accountability Form in order to monitor compliance with the medication schedule. All opened containers, together with remaining contents, and unopened containers will be kept by the Investigator in a secure, locked area until return to the drug supplier by the monitor or destruction by the site if agreed with the Sponsor. The Investigator will use the IMP only within the framework of this clinical study and in accordance with the existing study protocol.

If a subject is found to be persistently non-compliant with the study medication (defined as less than 80% or more than 120% compliant with the dosage schedule as measured at two separate visits), a decision will be made by the Investigator and Sponsor as to whether the subject should be withdrawn from the study treatment.

7.8 CONTINUATION OF TREATMENT

No further provisions are made for access to the study treatment under this protocol following the Week 52 / End of Study visit.

8 ENROLMENT AND RANDOMIZATION PROCEDURES

Full details of procedures will be provided in the Investigator Site File.

8.1 SCREENING

Subjects will be evaluated according to the inclusion and exclusion criteria (sections 6.3.1 and 6.3.2). Subjects will be deemed eligible for randomization if all inclusion criteria and no exclusion criteria are met. The Investigator is required to document all screened candidates considered for inclusion in this study. If excluded prior to randomization, the reasons for exclusion will be documented in the subject's medical notes and on the study screening log.

A subject may be retested once for laboratory criteria that do not meet protocol criteria so long as randomization occurs no more than 14 days from the initial test result (if eligible).

8.2 RANDOMIZATION

A final eligibility evaluation must be conducted immediately prior to randomization. If a subject is deemed eligible a centralized IXRS/randomization system will be used to assign the subject to ferric maltol or placebo.

Subjects will be randomized in a 2:1 ratio (ferric maltol:placebo) and will be stratified according to the subjects baseline Hb (<9.5 or ≥ 9.5 g/dL) and eGFR (≤ 30 or >30 mL/min/1.73m²).

8.3 BLINDING PROCEDURES

The Investigator and site staff, subjects, monitors, Sponsor and CRO staff will remain blinded to the treatment assignment during the conduct of the randomized phase of the study. The randomization codes will be released to the Sponsor for the purpose of the primary analysis only when the clinical database for the randomized phase of the study has been locked and a final Statistical Analysis Plan (SAP) is in place.

[figure not shown]
The randomization list is kept strictly confidential. It is accessible only to authorized persons who are not involved in the conduct and analysis of the study until time of un-blinding. The IXRS system will allow un-blinding by the vendor used by the Sponsor for reporting of suspected unexpected serious adverse reactions (SUSAR) as required by the regulatory agencies. The evaluation and decision as to whether a Serious Adverse Event (SAE) qualifies as an SUSAR is the responsibility of the Sponsor.

8.4 EMERGENCY UNBLINDING

Under normal circumstances, the blind should not be broken. The blind should be broken only if specific emergency treatment would be dictated by knowing the treatment status of the subject. It is highly unlikely that this situation will occur during this study. In such cases the Investigator can break the blind via the IXRS/randomization system. The system will encourage the Investigator to discuss the situation with Sponsor prior to breaking the code. Un-blinding will result in discontinuation of the subject from the study treatment and withdrawal from the study.

9 STUDY PROCEDURES

9.1 DESIGN SCHEMATIC

9.2 SCHEDULE OF ASSESSMENTS

PERIODS	SCREENING	RANDOMIZED TREATMENT					OPEN-LABEL TREATMENT					FOLLOW-UP
Visit Duration	1-14 days	16 weeks					36 weeks					14 days after last dose ³
Visit Number	1	2	3	4	5	6	7	8	9	10	11	12
Visit Name	Screening Period ¹	Randomization	Week 4	Week 8	Week 12 (Telephone)	Week 16 End of Randomized Treatment Period	Week 20 (Telephone)	Week 24	Week 32	Week 42	Week 52 End of Study ²	Telephone Follow-up
Visit Window		14 days from Screening ¹	±3 days of Randomization			±7 days of Randomization					14-21 days after last dose of study drug	
Informed Consent	X											
Demographics	X											
Medical History	X											
Concomitant Medications and Procedures	X	X ⁴	X	X	X	X	X	X	X	X	X	X
Physical Examination		X				X					X	
Vital Signs		X ⁴				X					X	
12-Lead ECG		X ⁴									X	
Urine Pregnancy Test	X	X ⁴	X	X		X		X	X	X	X	
Hematology, Chemistry and Iron markers	X	X ⁴	X	X		X		X	X	X	X	
Population PK Sampling ⁵		X ⁴	X			X					X ⁵	
eGFR	X					X					X ⁵	
Retention Samples ⁵		X ⁴				X					X	
Eligibility Confirmation and Randomization		X ⁴										
Dispense Study Drug		X	X	X		X		X	X	X		
Return Study Drug			X	X		X		X	X	X	X	
Adverse Events		X	X	X	X	X	X	X	X	X	X	X

Note: unscheduled visits may be required (e.g. repeat laboratory sampling or safety assessments).

1. *A subject may be retested once for laboratory criteria that do not meet protocol criteria so long as randomization occurs no more than 14 days from the initial test result (if eligible).*

Subjects who withdraw from the study before Week 16 should have assessments conducted per Week 16/ End of Randomized Treatment Period or per Week 52/End of Study if withdrawn after Week 16. Subjects who discontinue from study treatment prior to Week 16 will be encouraged to continue with study visits and assessments up to and including assessments at week 16.

2. *Follow-up call not required if the subject prematurely discontinued treatment and the End of Study Visit occurred 14 days after the last dose taken.*
3. *Laboratory sampling and assessments must be completed prior to the first dose of study treatment.*
4. *Population PK samples are only required at Week 52 / End of Study visit if the subject has discontinued treatment prior to Week 16. Retention samples only applicable for sites with access to a -70/80°C freezer for storage.*

9.3 DEMOGRAPHICS AND MEDICAL HISTORY

The following will be documented at screening and updated (if required) prior to randomization: year of birth, race and ethnicity, gender, all current medical conditions, all medical history relevant to IDA and or CKD regardless of onset and all known iron replacement therapies. Additionally, clinically significant medical history from the past 5 years will be documented including malignancies, sterilisations, hospitalizations, surgeries, ESA treatment history and the method of contraception for female subjects of childbearing potential.

9.4 PHYSICAL EXAMINATION

A brief physical exam will be conducted and will include body weight, height (screening only) and an assessment of general appearance, skin, head, eyes, ears, nose and throat, cardiovascular, respiratory, abdominal, gastrointestinal and musculoskeletal. The Investigator will record any clinically significant finding as an AE.

9.5 CONCOMITANT MEDICATIONS AND PROCEDURES

The following will be documented at screening and updated (if required) prior to randomization: all current medications at the time of screening or stopped within 12 weeks of screening and any medical procedure performed within 4 weeks prior to screening.

The following will be documented throughout the study: any medications initiated, stopped or with dose and/or frequency changes throughout the study. Any medical procedure performed throughout the study.

Medical procedures to be documented will include any therapeutic intervention such as surgery/biopsy, physical therapy or diagnostic assessment (e.g. blood gas measurement).

9.6 VITAL SIGNS

Blood pressure and heart rate will be measured after the subject has been supine for 5 minutes.

9.7 12-LEAD ECG

A 12-lead ECG will be conducted after the subject has been supine for 5 minutes.

9.8 LABORATORY ASSESSMENTS

All analyses will be conducted via the central laboratory unless specified. Planned assessments are for both efficacy and safety purposes. The primary endpoint of the study, hemoglobin, will be analysed via the hematology panel and will be reported in g/dL.

Investigators will review, sign and date all lab results upon receipt from the central laboratory. If a value is flagged as outside of the normal range, the Investigator must document the abnormality as 'clinically significant' (CS) or 'non-clinically significant' (NCS).

The signed paper copy of the laboratory report is retained at the investigational site. The electronic file transferred from the central laboratory to the Sponsor will be considered source data for laboratory analysis.

Full details of the required sample collection and processing procedures will be described in the Central Laboratory Manual for the study.

9.8.1 Hematology

Hemoglobin, hematocrit, red blood cell count, red blood cell Hb, mean corpuscular hemoglobin (MCH), mean corpuscular hemoglobin (MCHC), white blood cell count (total and differential), absolute reticulocyte count, mean reticulocyte hemoglobin content (CHr), mean cell volume (MCV) and platelet count.

9.8.2 Chemistry

ALT, AST, alkaline phosphatase gamma-glutamyl transpeptidase (GGT), total bilirubin, creatinine, amylase, blood urea nitrogen (BUN), phosphorous, sodium, potassium, chloride, calcium, total cholesterol, uric acid, glucose, total protein, albumin. The following will be analysed during screening only: vitamin B12, C-reactive protein (CRP) and folate.

9.8.3 Iron Markers

Serum iron, ferritin, transferrin, total iron-binding capacity and TSAT. Soluble transferrin receptor will be analysed at baseline, week 4, week 16 and week 52 only.

9.8.4 Estimated Glomerular Filtration Rate (eGFR)

Analysed at screening, week 16 and week 52/End of Study only via the central laboratory using the Modified Diet in Renal Disease equation (MDRD).

9.8.5 Population Pharmacokinetics (PK)

Population based PK analysis of maltol and key metabolites (maltol glucuronide) will be conducted. Serum iron will also be analysed using the results collected via iron marker samples (Section 10.8.3). Single point sampling at specified visits will be conducted in accordance with FDA Guidance on Population Pharmacokinetics (February 1999). Subjects will be instructed to hold the morning dose of study drug until after the study visit. The date and time (hour and minute) of the last dose of study drug, prior to sampling, is to be recorded by the subject.

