4.4 DOSE SELECTION AND RESULTS OF PREVIOUS CLINICAL STUDIES

Ferric maltol is not absorbed systemically as an intact complex and traditional PK studies may not provide the relevant information (Barrand 1991). Therefore, a model was developed to determine the optimal dose. Data from 6 previous studies of ferric maltol in subject with IBD and IDA were used to estimate absorption rates in the study population. Using these data, the model suggested that in a compliant study population, 30 mg ferric maltol bid would result in correction of baseline anemia in the majority of subjects.

An open-label, randomized Phase 1 study evaluated the pharmacokinetics of ferric maltol and its effect on iron indices in IBD patients with iron deficiency (with or without anemia). Twenty four subjects received ferric maltol 30, 60, or 90 mg bid over an 8-day period. Pharmacokinetics and iron uptake were assessed on Days 1 and 8. Ferric maltol showed predictable pharmacokinetics, with linear increases in exposure, no accumulation over 7 days, and improvements in iron uptake across the dose range 30–90 mg bid.

The dose chosen for Phase 3 studies is 30 mg bid ferric maltol, or 60 mg elemental iron total daily dose.

A Phase 3 study has been completed in subjects with IDA and Inflammatory Bowel Disease (IBD), who are intolerant of oral iron products or are unsuitable for treatment with them (ST10-01-301 and ST10-01-302; Gasche 2014). 128 subjects were randomized to 12 weeks of blinded medication (30mg bid ferric maltol or matched placebo capsule) followed by a 52 week open-label extension period; during which all available subjects received ferric maltol at the same dose. 87% and 82% ferric maltol and placebo treated subjects, respectively, completed the 12 week double blind period. The difference between the treatment groups in mean Hb from baseline to week 12 was 2.25g/dL (ANCOVA $p < 0.0001$). Hb increased to normal values at week 12 in 65% of ferric maltol group and 10% of placebo subjects. When the placebo subjects were transferred to ferric maltol treatment in the open-label phase, there was a sharp rise in Hb levels that mirrored the response in the ferric maltol group in the double-blind phase. There were further increases in Hb up to 48 weeks of treatment and no indication of any reduction in efficacy over the full 64 week treatment period.

Refer to the Investigator Brochure for further information.

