9.8.6 Retention Samples

Serum and plasma samples will be collected for future analysis by sites with access to a -70/80°C freezer only. No genetic testing will be completed on any samples obtained during the study. Samples will be stored for a maximum of 5 years following the last study sample taken. Analyses will be restricted to safety related analyses and exploratory efficacy related analyses of ferric maltol related to the treatment of IDA.

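### Do pre-dose samples alone leave the population PK endpoint unable to deliver what the plan asks of it?

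*Combined protocol and SAP*

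**What the plan says.** Section 5.2 includes pharmacokinetics in the secondary objective. Section 5.5 sets the PK endpoint as a population analysis of maltol, maltol glucuronide and serum iron, and names no parameter.

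On sampling, section 9.8.5 says "Single point sampling at specified visits will be conducted" and "Subjects will be instructed to hold the morning dose of study drug until after the study visit". It cites FDA guidance on population pharmacokinetics as the basis and has subjects record the time of their last dose. For iron it says "Serum iron will also be analysed using the results collected via iron marker samples".

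The schedule in section 9.2 places PK samples at Randomization, Week 4, Week 16 and Week 52/End of Study. The first carries no exposure information, because "Laboratory sampling and assessments must be completed prior to the first dose of study treatment". The last is conditional: "Population PK samples are only required at Week 52 / End of Study visit if the subject has discontinued treatment prior to Week 16". That leaves Weeks 4 and 16 as the scheduled on-treatment samples.

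Stored samples are not a substitute. Section 9.8.6 says "Analyses will be restricted to safety related analyses and exploratory efficacy related analyses of ferric maltol related to the treatment of IDA". Section 9.8 adds "Full details of the required sample collection and processing procedures will be described in the Central Laboratory Manual for the study".

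**The concern.** The synopsis has the second daily dose taken at bedtime. With the morning dose held, both on-treatment samples fall well after that dose, and no sample is scheduled soon after one. If absorption is over by the time of the draw, a late concentration shows only the declining tail, and many combinations of absorption rate, clearance and volume fit the same tail.

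Pharmacokinetics is a stated objective, and the population differs from the one studied before. The earlier PK study described in section 4.4 had 24 subjects with IBD. This trial enrols subjects with eGFR from 15 to below 60, and section 4.3 says that the glucuronide leaves the body in urine. Peak exposure and absorption in CKD would have to be borrowed. Once the Week 4 and Week 16 samples are in the freezer, the missing early samples cannot be recovered.

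**Working it through.** **Plan's own figure.** The documents state no PK precision, PK sample size or exposure value, so there is nothing to reproduce. What can be checked is what two late samples per subject can estimate.

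**Inputs from the documents.** Twice-daily dosing; two on-treatment samples per subject, both pre-dose; 90 active subjects (section 11.1, after the assumed 20% drop-out).

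**Assumptions, not in the documents.** Absorption rate ka of 1, 2 or 4 per h (for the glucuronide this covers absorption and formation together); half-life 1, 2, 4 or 6 h; draws uniform over 8-12, 8-14 or 10-14 h after the last dose; between-subject SD 30% on each parameter; residual error 20%; every sample quantifiable. That makes 4 × 3 × 3 = 36 scenarios. Serum iron is endogenous and is not modelled.

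**Model.** One compartment, steady state, τ = 12 h, ke = (CL/F)/(V/F) = ln 2 / half-life:

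`C(t) = ka·D / [(V/F)·(ka − ke)] × [e^(−ke·t)/(1 − e^(−ke·τ)) − e^(−ka·t)/(1 − e^(−ka·τ))]`

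Precision comes from the first-order population information matrix on the log parameters, `F = Σ Jᵀ(JΩJᵀ + σ²I)⁻¹J`, with Ω = 0.3²·I and σ = 0.2. The relative SE is the square root of the diagonal of F⁻¹.

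**Which scenarios meet the condition.** At ka = 1 per h and half-life 1 h, ke = 0.693 and ka/ke = 1/0.693 = 1.44. That is not rapid absorption relative to elimination, so its three scenarios (one per sampling window) are set aside, leaving 33. They matter: with them in, the floor for troughs alone is about 85% and the upper limits under a 30% prior are 43% (CL/F) and 41% (V/F).

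| Design, 90 active subjects, 33 scenarios | CL/F | V/F | ka |
|---|---|---|---|
| Two troughs, all parameters free | about 240% or more | about 230% or more | about 500% or more |
| Two troughs, ka fixed | 7-19% | 13-28% | not estimated |
| Two troughs, outside prior on ka, SE 30% | 8-24% | 14-29% | from the prior |
| One trough plus one sample at 0.5-4 h | 3.5-6% | 4-10% | 12-60% |

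The first row confirms that troughs alone do not identify the model. A separate calculation with 112 subjects (two thirds of 168), unequal dosing intervals and a larger SD on ka also gave relative SEs for ka of about 257% or more. Rows two and three show that the planned samples become usable once absorption is supplied from outside.

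**If the outside absorption value is wrong.** Take a true ka of 2 per h and refit CL/F and V/F to the 8-14 h concentrations with ka set to 1 or 4. Every trough is reproduced within 0.2%, so the data cannot reveal the error. AUC over a dosing interval is D/(CL/F).

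| Half-life | Peak error, ka = 1 / ka = 4 | AUC error, ka = 1 / ka = 4 |
|---|---|---|
| 2 h | −34% / +26% | −20% / +10% |
| 4 h | −20% / +14% | −9% / +5% |
| 6 h | −14% / +9% | −6% / +3% |

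**Are troughs likely to be measurable?** Section 4.4 reports for the earlier study: "Ferric maltol showed predictable pharmacokinetics, with linear increases in exposure, no accumulation over 7 days". The accumulation ratio is 1/(1 − 0.5^(12/half-life)): 1.02 at 2 h, 1.14 at 4 h and 1.33 at 6 h. So the statement fits a half-life of about 4 h or less. With ka/ke of 5-10, the share of peak left at 10 h is 4.5-5.8% at a half-life of 2 h and 25-33% at 4 h. Reduced renal excretion could raise glucuronide troughs here. No assay limit is given, so this stays open.

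**The case for a change.** The best case for changing the plan is that the remedy looks cheap: move one of the two planned PK samples to a window after the morning dose taken at the visit, and keep the iron-marker draw pre-dose. No visit and no PK sample is added, and ka becomes estimable within this trial. The schedule reading and the identifiability argument behind this both stand.

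The argument for acting is weaker, for four reasons.

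- Nothing promised is lost. Section 5.5 commits to no peak, absorption or AUC parameter, and no decision described in the documents depends on peak exposure. Section 4.4 itself doubts that conventional PK studies are informative for a complex that is not absorbed intact, and bases the dose on a model of absorption.
- Reduced renal elimination of the glucuronide is the natural CKD question. It concerns clearance and average exposure, which the trough design handles much better than peak.
- The gain is mainly for one analyte. Section 4.3 reports that parent maltol was not detected in early studies, and serum iron would stay pre-dose. Even with the early sample, the relative SE of ka reaches 60% in some scenarios.
- The cost is real: a second needle draw, an observed dose on an empty stomach and a longer stay, across about 35 sites.

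The condition is also unproven. With slow absorption (ka 0.2-0.3 per h, half-life 4-6 h, 8-14 h window), troughs alone would give CL/F to 16-24% without outside data, although V/F and ka would stay above 100%.

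**Conclusion.** The plan's samples cannot by themselves measure absorption or peak exposure of maltol and its glucuronide if absorption is rapid relative to elimination. That limits the scope of the PK conclusion and is not an error in the plan. Late sparse sampling with absorption taken from richer earlier data is an accepted population PK approach. Under the assumed kinetics it yields CL/F to about 7-25% and V/F to about 13-29% with 90 active subjects. An analyst would fix ka or give it a prior from the earlier PK study, and would report peak and absorption in CKD as borrowed values. The protocol does not say that this will be done, but section 11.2.2 defers the detail of secondary analyses to the SAP, and writing it down earlier would not change the data collected. The primary endpoint is untouched.

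The conclusion rests on quantifiable troughs, a one-compartment model and assumed rates, none of which the documents settle. If glucuronide troughs proved unquantifiable, the PK endpoint would deliver little for that analyte.
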